## 9.2 Survey of subject background

The following background information of subjects participating in the clinical trial should be included:

- Subject identification code
- Sex
- Age at the time of consent
- Consent acquisition date
- Major underlying diseases/complications present in patient at the time of consent acquisition

clinical trial protocol 番号 : YCU-21001

- Drug allergy

### 9.3 Observation/examination items and endpoints related to efficacy evaluation

- Rate of change and amount of change in liver fat content (%) measured by MRI-PDFF at 16 weeks from baseline
- Rate of change from baseline in measurements at 16 weeks includes:
  1. ALT, AST,  $\gamma$ -GTP
  2. Weight
  3. Blood lipids (chylomicron cholesterol, chylomicron triglyceride, lipoprotein cholesterol, LDL triglyceride, VLDL cholesterol, VLDL triglyceride, free cholesterol, apoprotein A1, apoprotein B, adipsin, free fatty acid)
  4. Insulin resistance (HOMA-IR)
  5. Liver hardness (MRE)
  6. Fibrosis markers (ELF score, Fibrosis-4 (FIB-4))
- Rate of change of each clinical laboratory test value (inflammation, endocrine, fibrosis, etc.)

### 9.4 Observation/examination items and endpoints related to safety evaluation

- Occurrence rate of adverse events

### 9.5 Primary endpoint

- Percentage of those where the liver fat content (%) measured by MRI-PDFF at 16 weeks decreased by 3.46% or more from baseline (%)

#### 【Setting basis】

To evaluate hepatic fattening of NAFLD, evaluation using MRI-PDFF is considered appropriate for the pathological condition.

Recent reports have indicated that the diagnostic ability of MRI-PDFF is superior to that of CAP as a diagnostic assessment of fattening of the liver (13). Liver biopsy is commonly used to assess hepatic fat mass. However, it is invasive and is not suitable for monitoring. Image evaluation by MRI-PDFF is stable and highly reproducible. In addition, since the judgment of fat deposition differs depending on the collection site in liver biopsy, MRI-PDFF, which enables easy quantitative evaluation, is considered appropriate (14) -17).

The 24-week MOZART placebo-controlled randomized controlled trial explored the correlation between histological changes by liver biopsy and hepatic fat content using MRI-PDFF to examine the effect of ezetimibe on NASH. The trial reported an estimated cutoff point of -3.46% for changes in liver fat content from baseline that optimally distinguished between histological responders and non-responders (12). Patients with a change from baseline of  $\leq -3.46\%$  in hepatic fat content measured by MRI-PDFF were 4.3 times more likely of being a true histological responder than a false positive.

The purpose of this clinical trial is to confirm a POC. Based on this, we plan to conduct a study to confirm the dose setting in the next phase, and to conduct a verification test of efficacy by evaluation including liver biopsy (confirmation of fibrosis).

### 9.6 Secondary endpoints

clinical trial protocol 番号 : YCU-21001

1) Amount of change and rate of change from baseline in the measured values at 16 weeks were determined. The rate of change is defined as (value at 16 weeks - baseline value) / (baseline value).

The following items were measured:

- Percentage of subjects where the liver fat content (%) measured by MRI-PDFF at 16 weeks decreased by  $\geq 3.46\%$  from baseline for the 4 mg and 8 mg groups
- Amount of change and rate of change in liver fat content measured by MRI-PDFF
- Rate of change in ALT, AST, and  $\gamma$ -GTP
- Rate of change in weight
- Rate of change in blood lipids (chylomicron cholesterol, chylomicron triglyceride, lipoprotein cholesterol, LDL triglyceride, VLDL cholesterol, VLDL triglyceride, free cholesterol, apoprotein A1, apoprotein B, adipsin, free fatty acid)
- Rate of change in insulin resistance (HOMA-IR)
- Rate of change in liver hardness (MRE)
- Rate of change of fibrosis markers (ELF score, Fibrosis-4 [FIB-4])

2) Search for new markers related to liver disease and obesity metabolic disease

## 10 Pharmacogenomics

### 10.1 Somatic genetic testing

This testing is conducted to evaluate the effects of disease susceptibility genes (PNPLA3, TM6SF2) in NAFLD on clinical endpoints and drug responsiveness. These assessments are exploratory and will not be included in the summary report.

#### 10.1.1 Blood sample collection time/sample processing

Blood samples are collected at the time specified in "エラー! 参照元が見つかりません。 エラー! 参照元が見つかりません。". Blood samples are processed by following the procedure manual specified separately. The total amount of blood collected is approximately 5 mL.

#### 10.1.2 Specimen storage and management

Specimens should be stored with the subject identification code. Specimens should be stored for up to 5 years after final analysis before disposal. The subject identification code is also assigned to the data generated from the sample.

Excess specimens will be stored until they are discarded under the control of an authorized person in the Yokohama City University School of Medicine Department of Gastroenterology and Hepatology. A comparison table of subject identification code and information that can directly identify the subject should be stored appropriately together with the sample management table.

#### 10.1.3 Use and disposal of specimens

Surplus samples are stored together with the sample management table for 5 years. Specimens that have passed the storage period should be discarded in anonymized form unless there is a specific reason to keep them.

If consent is withdrawn, the identification code of the subject is deleted and discarded appropriately. Specimens that have been stored for more than 5 years since the final analysis should be discarded unless there is a specific reason to keep them. Use of surplus samples for purposes other than the research purpose shall be approved by the relevant ethics review committee by creating a new research protocol.

clinical trial protocol 番号 : YCU-21001

#### 10.1.4 Withdrawal of consent for use of specimens

If the subject withdraws consent to use the provided sample, the sample will be disposed of and will not be used in the study. However, this does not apply if the research results have already been announced at the time of withdrawal of consent. If the measurement/analysis has already been performed, it will continue to be used to maintain the integrity of the existing analysis.

The principal investigator will confirm that the following points have been implemented:

- The withdrawal of the subject's consent regarding the use of the provided sample shall be reported immediately. If the sample collected from the subject is stored in the implementing medical institution, it should be immediately identified and disposed of. This process will be recorded in the trial information.
- The withdrawal of consent is immediately notified to the medical institution storing the specimen. The specimen is then disposed of, and a record of the disposal is made and submitted to the medical institution coordinating the study.
- The subject is informed that the specimen has been disposed of.
- The specimen must be discarded by the end of a specific period, as described in the explanatory document.

### 11 Ensuring subject safety

#### 11.1 Basic items

When registering subjects, the selection and exclusion criteria must be met. Care is taken not to register subjects who are not included in this study.

During the clinical trial period, the principal investigator, sub-investigator, or clinical trial collaborators shall be in constant contact with the subject to ensure safety of the subject. In addition, when adverse events occur, the safety of the subject is ensured by providing appropriate medical care.

#### 11.2 Definitions

##### 11.2.1 Definition of adverse event

Adverse events are any unwanted or unintended signs (including laboratory test values, abnormal vital signs), symptoms, or illness that occur during the trial. The causal relationship with the investigational drug does not matter.

Symptoms and diseases that have occurred before the start of the clinical trial should be recorded as complications in the case report form and should not be classified as adverse events. However, if complications worsen during the clinical trial period, they will be treated as an adverse event. The day when the deterioration is confirmed is the onset date of the adverse event. For events that have multiple symptoms (including signs and abnormal laboratory test values) and have a diagnosis/disease name, the diagnosis/disease name is recorded as an adverse event name in the case report form.

##### 11.2.2 Evaluation of adverse event

Principal investigators, etc. determine the severity of adverse events with reference to Table Table 11.2.2-1.

Table 11.2.2-1 Severity criteria

Classification	Criteria
1 Mild	Does not interfere with daily life (eating, sleeping, bathing, going out, work, exercise, etc.)
2 Moderate	Interferes with daily life (eating, sleeping, bathing, going out, work, exercise, etc.)

clinical trial protocol 番号 : YCU-21001

3 Advanced	Daily life (meal, sleep, bathing, going out, work, exercise, etc.) is impossible
------------	--

The "diagnosis name" is generally entered for the name of the adverse event, but if a definitive diagnosis cannot be made, use "sign" or "symptom". It is desirable to describe as much as possible corresponding to "ICH Medical dictionary for regulatory activities / J (MedDRA / J)".

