## List of definitions of abbreviations and terms

## Abbreviations

Abbreviations	Expressions or explanations not abbreviated	
	English term	Japanese name or explanation
CTCAE	Common terminology criteria for adverse events	Common terminology criteria for adverse events
DPP-4	Dipeptidyl peptidase-4	Dipeptidyl peptidase-4
EDC	Electronic data capture	Electronic data capture
EOT	End of treatment	End of treatment
FAS	Full analysis set	Full analysis set
GCP	Good clinical practice	Good clinical practice
HIV	Human immunodeficiency virus	Human immunodeficiency virus
ICH	International Council for Harmonisation of Technical Requirements for Pharmaceuticals for Human Use	International Council for Harmonisation of Technical Requirements for Pharmaceuticals for Human Use
MedDRA / J	Medical dictionary for regulatory activities/J	Medical dictionary for regulatory activities/J
MRE	Magnetic resonance elastography	Magnetic resonance elastography
NAFL	Non-alcoholic fatty liver	Non-alcoholic fatty liver
NAFLD	Non-alcoholic fatty liver disease	Non-alcoholic fatty liver disease
NASH	Non-alcoholic steatohepatitis	Non-alcoholic steatohepatitis
NASH CRN	NASH clinical research network	NASH clinical research network
NYHA 分類	New York heart association functional classification	New York heart association functional classification
POC	Proof of concept	Proof of concept
PPS	Per protocol set	Per protocol set
SAS	Safety analysis set	Safety analysis set
SGLT2	Sodium-glucose cotransporter	Sodium-glucose cotransporter

clinical trial protocol 番号 : YCU-21001

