#### 13.4.3 Analysis of safety endpoints

In each group, the number and proportion of adverse events are calculated according to the event and the severity specified in Section 11.2.2.

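### Adverse event severity is graded only by interference with daily life, so a symptom-free laboratory or vital-sign abnormality of any size meets only the Mild criterion in the severity breakdown

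*Protocol*

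**What the plan says.** Section 11.2.1 defines adverse events as "any unwanted or unintended signs (including laboratory test values, abnormal vital signs), symptoms, or illness that occur during the trial", so a measured abnormality counts without any symptom. The same section adds that when several signs or symptoms have a diagnosis, the diagnosis is recorded as the event name. Section 11.2.2 likewise prefers a diagnosis name and falls back on a sign or symptom when no definitive diagnosis can be made.

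Section 11.2.2 then gives one severity instrument for all events: "Principal investigators, etc. determine the severity of adverse events with reference to Table Table 11.2.2-1". Its three levels are:

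- Mild: "Does not interfere with daily life (eating, sleeping, bathing, going out, work, exercise, etc"
- Moderate: "Interferes with daily life (eating, sleeping, bathing, going out, work, exercise, etc"
- Advanced: "Daily life (meal, sleep, bathing, going out, work, exercise, etc.) is impossible"

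Section 9.4 names one safety endpoint, the rate at which adverse events occur. For the analysis, section 13.4.3 states that in each group "the number and proportion of adverse events are calculated according to the event and the severity specified in Section 11.2.2". CTCAE appears in the abbreviation list ("Common terminology criteria for adverse events"), but no section of the protocol text applies it.

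**The concern.** The definition of an adverse event and the scale used to grade it do not fit each other. The definition admits events that exist only as a number on a laboratory report or a blood-pressure reading. The scale asks only what the patient can or cannot do, and no level refers to the size of a deviation, the need for treatment or medical risk.

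This matters more here than in many trials. The patients have liver disease and take a drug that lowers blood pressure, with other antihypertensives allowed to continue at a constant dose (section 8.3.2). Changes in transaminases, creatinine, blood pressure and pulse may well appear first, or only, as measurements. Section 1.5.2 itself says that adverse drug reactions in this population may differ in severity from those in the approved population, and asks for close observation of metabolic values. A reader of the severity table would take Mild to mean a small abnormality, when for a symptom-free finding it means only that daily life was not disturbed.

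**Working it through.** No sample size, power or error rate is involved, and the plan states no figure to reproduce. The check applies the grading rule as written and follows the grade to the places where it is used.

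**Step 1: apply the table to a symptom-free abnormality.**

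| Level | Criterion in Table 11.2.2-1 | Met without symptoms or restriction? |
|---|---|---|
| 1 Mild | no interference with daily life | yes |
| 2 Moderate | interference with daily life | no |
| 3 Advanced | daily life impossible | no |

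Only the first row is met, and the size of the abnormality does not enter. As a hypothetical illustration, exclusion criterion 5(1) lets a man enter with ALT up to 430 IU/L. A symptom-free doubling to 2 × 430 = 860 IU/L and a trivial symptom-free rise recorded as an event both fall in the Mild row.

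**Step 2: look for an exception.** If the abnormality leads to admission or restricted activity, that consequence can lift the grade. No other criterion in the table does so.

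**Step 3: follow the grade.** Section 13.4.3 tabulates by event and by this grade, so the abnormality enters the severity breakdown as Mild.

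**Step 4: see what does not depend on the grade.**

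- Occurrence rate (9.4) and counts by event (13.4.3): an event counts once whatever its grade.
- Seriousness (11.2.4): defined separately. It includes possible death and possible injury, so an extreme symptom-free value can qualify.
- Important adverse events (11.2.5): non-serious events for which the drug had to be stopped.
- Causality (11.2.3) and subject termination (12.1): neither refers to the severity grade.
- ALT, AST and γ-GTP: their rate of change is a secondary endpoint (9.6), summarised by group and compared by t-test (13.4.2). This would show a mean shift but can miss a single extreme patient. The protocol's outline has no such analysis for creatinine, pulse or blood pressure.

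**Step 5: see what can be counted.** After dosing starts, Biochemical test 1 is taken at V4 to V8 (5 visits) and vital signs at V3 to V8 (6 visits). For 28 completers that gives 28 × 5 = 140 chemistry panels and 28 × 6 = 168 sets of vital signs. These are occasions on which an abnormality could be found. They do not estimate how many events would be graded misleadingly, and the protocol gives no rate from which to derive one.

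**The case against.** The strongest reply is that little depends on this grade. The safety endpoint is an occurrence rate, which severity does not affect. No stopping, reporting or causality rule uses the severity level. Extreme values have their own routes as serious or important events, and transaminase changes are analysed as secondary endpoints. A functional three-level scale is also a legitimate choice, and investigators grade with reference to the table, which leaves some room for judgement.

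Most of this stands and sets the limits of the point. It does not remove it. Neither the serious nor the important category is a stated axis of 13.4.3, and neither grades values that fall short of it. Judgement outside the table has no criterion to follow, so it would vary between assessors.

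A reader might infer several stronger things that the protocol does not support:

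- **That the safety conclusion as a whole is biased.** Only the severity breakdown is affected.
- **That this is the trial's only safety analysis.** It is the only one in section 13.4, which section 13.4 itself calls an outline. The separate statistical analysis protocol may add laboratory and vital-sign summaries.
- **That the two dose groups cannot be separated on severity.** Symptomatic events can still be compared. The limit concerns symptom-free measured abnormalities, in a descriptive table with 14 patients per group.
- **That 140 panels and 168 vital-sign sets measure the damage.** They are measurement occasions, and the affected events could be close to none.
- **That the CTCAE entry shows an intended rule that was dropped.** An unused abbreviation is weak evidence: creatine kinase is also listed but is absent from the laboratory items in Table 9.1-2.

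**Conclusion.** The point holds within narrow limits. As written, a symptom-free laboratory or vital-sign abnormality of any size meets only the Mild criterion, unless its consequences restrict daily life, and it enters the severity breakdown as Mild. For these events the breakdown carries no information about magnitude.

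The number of events affected is unknown. The efficacy results, the adverse event occurrence rate, the counts by event, and the serious and important event routes do not change. The conclusion assumes that investigators grade by the table and that no other grading instruction overrides it. The protocol shows none.

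This cannot be left to the analysis plan. The plan can add summaries of measured values, but the grade is assigned by the investigator during the trial under section 11.2.2. The change is worth making because safety is part of the stated purpose (3.1) and the cost is small.

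**What to change.** In section 11.2.2, state that any adverse event resting on a laboratory or vital-sign measurement is graded by one named version of a published scale that does not depend on interference with daily life. CTCAE is an obvious candidate, since it is already in the abbreviation list. The protocol does not reproduce its thresholds, so the team should confirm that the chosen version grades the relevant items by measured value.

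The wording must cover such events whether they are recorded as a sign or under a diagnosis name. Sections 11.2.1 and 11.2.2 prefer diagnosis names, so a rule limited to laboratory values would send a transaminase rise entered as a liver diagnosis, or low blood pressure entered as hypotension, back to the daily-life scale.

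Keep Table 11.2.2-1 for symptomatic events. Where an event has both a measured abnormality and symptoms, record both grades. In section 13.4.3, tabulate both scales by group.

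The cost is one paragraph in 11.2.2, one EDC field and one additional table. The downside is that the report will carry two severity scales, and each table must say which one it uses.

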### 11.2.3 Determination of causality

The principal investigator or sub-investigator determines the causal relationship with the investigational drug by referring to Table 11.2.3-1. Among adverse events, those for which a causal relationship with the investigated drug cannot be excluded are considered adverse drug reactions.

Table 11.2.3-1 Criteria for determining causality with investigational drug

Classification	Criteria
1. Can be denied	There is no reasonable possibility that the investigational drug caused the adverse event
2. Cannot be denied	There is at least a reasonable possibility for the causal relationship between investigational drugs and adverse event

### 11.2.4 Definition of serious adverse event

A serious adverse event is an adverse event that corresponds to the following:

- Death
- Possibility of death
- Hospital or clinic admission, or extension of hospital stay, required for treatment
- Injury
- Possibility of injury
- Serious issue according to the above items
- Congenital illness or abnormality in later generations

However, the following are excluded:

- 1) Hospitalization planned before participating in the clinical trial
- 2) Hospitalization not related to adverse events, such as examination purposes
- 3) Hospitalization within 24 hours for follow-up purposes only

### 11.2.5 Definition of important adverse event

For those who conduct their own clinical trials, regarding the adverse events (excluding serious adverse events) that occurred in this clinical trial, the adverse events that had to be terminated using investigational drugs are regarded as important adverse events.

### 11.3 Response when serious adverse event occurs

The principal investigator or sub-investigator will take appropriate measures when a serious adverse event occurs. The principal investigator will immediately report the details to the head of the medical institution coordinating the trial and the funder using the unified "(Medical) Form 12". The detailed reporting procedure shall be described in the "Manual for handling safety information".

If a serious adverse event requires reporting to the Minister of Health, Labor and Welfare, it is reported within a specified date according to the "Manual for handling safety information".

### 11.4 Re-definition of adverse event into standard terms

The terms used by the principal investigator and others are coded to correspond to the International Council for Harmonisation of Technical Requirements for Pharmaceuticals for Human Use (ICH)

clinical trial protocol 番号 : YCU-21001

Medical dictionary for regulatory activities/J (MedDRA/J) for all adverse events that occur. The MedDRA / J version shall be the latest available version or the previous version.

clinical trial protocol 番号 : YCU-21001

## 12 Termination criteria and procedure

### 12.1 Termination criteria

The principal investigator or sub-investigator terminates the participation of a subject enrolled in a clinical trial if any of the following apply:

1. When a subject requests to be withdrawn from the clinical trial.
2. If it is found after registration that the subject does not meet the inclusion criteria or conforms to one or more exclusion criteria
3. When drugs or therapies whose concomitant use is prohibited are administered.
4. When it is judged that it is difficult to continue the clinical trial due to the occurrence of adverse events or for other reasons.
5. When the continuation of the clinical trial is judged to be inappropriate by the principal investigator or others.

[Setting basis for termination criteria]

1. This is explained when obtaining consent and was set as the subject's right.
2. Subjects who should not be administered were set because the clinical trial should be terminated early.
- 3.4. Set for safety reasons.
5. Other than the above, termination can be based on the judgment of the principal investigator or sub-investigator.

